3.1.1.8 Investigator's Global Assessment (IGA)

At each visit, the investigator will assess the overall status of the subject's skin for AD using the IGA as per the scale noted in Appendix III. The IGA is a static assessment of how the subject's overall skin is observed at the time of the current visit. Scores or severity from prior visits should not be considered. The IGA scores for each visit will be documented on the source and the Case Report Form. Subjects must have a score of mild to moderate AD on IGA in order to be enrolled in the study.

- 3.1.1.9 **Pruritus Assessment**: Pruritus will be assessed by questioning the subject or the subject's guardian regarding the intensity of overall itching/scratching/discomfort in the 24 hours prior to the visit using the scale mentioned in Appendix II.
- 3.1.1.10 **Local Application Site Reactions**: Subjects will also be assessed at screening for evaluation of pre-treatment local application site reactions. At each study visit, the investigator will evaluate any application site reactions with separate severity scores for dryness, burning/stinging, erosion, edema, and pain. At each visit the reactions will be

CONFIDENTIAL

Version 2.0 Dated 14 Oct 2016

noted and classified as mild, moderate or severe. Refer to Appendix IV Local Irritation Scale (LIS) for scoring of application site reactions.

- 3.1.1.11 **Physical Examination**: Subjects will undergo a general physical examination. A detailed dermatological examination is required. A full body dermatologic examination will assess if the subject has any dermatologic malignancies. If the subject does have a dermatologic malignancy, they should not be enrolled. The following systems should also be evaluated: head, ears, nose, throat, eyes, central nervous system, respiratory, cardiovascular, gastrointestinal, and musculoskeletal.
- 3.1.1.12 **Concomitant Medication:** History concomitant medications used will be obtained for at least the past 30 days. The start and stop date of medication use will be collected in addition to the reason for use. See section 6.3.

3.1.1.13 Screening Criteria:

Subjects will be evaluated to confirm that they meet the following screening criteria.

- Non-immunocompromised male or female aged 8 years and older
- Clinical diagnosis of mild to moderate atopic dermatitis (AD), as defined by the criteria of Hanifin and Rajka
- Failed to respond adequately to other topical prescription treatments for AD, or for whom those treatments are not advisable (The subject/guardian's verbal report of failure to other topical prescription treatments for AD will be adequate.)
- An Investigator's Global Assessment (IGA) of disease severity of mild or moderate at baseline (score of 2 or 3)
- Affected area of AD involvement at least 5% body surface area (BSA)
- Expected to be able to meet inclusion and exclusion criteria (See section 4.1.) after minimum 7 days of continuous treatment with a bland emollient (e.g. Cetaphil® Lotion).
- 3.1.1.14 **Bland emollient distribution**: Subjects who meet Screening Criteria will receive a bland emollient (e.g. Cetaphil® Lotion) to use at least once per day over seven days. Those subjects who have already been using bland emollient as standard of care don't need study bland emollient dispensation. In such case, procedures of Visit 1 (V1) and Visit 2 (V2) can be combined in one visit, if desired.
- 3.1.1.15 **Schedule Next Visit**: Subjects will be instructed on care until their next visit. Subjects should return the provided bland emollient at the next visit. Subjects should be advised that they will be evaluated again at the next visit to confirm their eligibility for study treatment.

CONFIDENTIAL

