The use of Pimecrolimus Cream, 1% may cause local symptoms such as skin burning (burning sensation, stinging, soreness) or pruritus. Localized symptoms are most common during the first few days of Pimecrolimus Cream, 1% application and typically improve as the lesions of atopic dermatitis resolve.

CONFIDENTIAL

Version 2.0 Dated 14 Oct 2016

Drug Interactions

Potential interactions between Pimecrolimus Cream, 1% and other drugs, including immunizations, have not been systematically evaluated. Due to low blood levels of pimecrolimus detected in some patients after topical application, systemic drug interactions are not expected, but cannot be ruled out. The concomitant administration of known CYP3A family of inhibitors in patients with widespread and/or erythrodermic disease should be done with caution. Some examples of such drugs are erythromycin, itraconazole, ketoconazole, fluconazole, calcium channel blockers and cimetidine.

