3.1.2 V2 - Baseline and Randomization Visit (Day 1)

The study specific procedures to be evaluated at baseline visit are:

- 3.1.2.1 Vital signs (See section 3.1.1.4)
- 3.1.2.2 Signs and symptoms evaluation (See section 3.1.1.6)
- 3.1.2.3 Body surface area assessment (See section 3.1.1.7)
- 3.1.2.4 Investigator's Global Assessment (IGA) (See section 3.1.1.8)
- 3.1.2.5 Pruritus Assessment (See section 3.1.1.9.)
- 3.1.2.6 Local application site reactions (pre-treatment) (See section 3.1.1.10)
- 3.1.2.7 **Urine pregnancy test** will be conducted for female subjects of child bearing age prior to dosing.
- 3.1.2.8 **Adverse Event Assessment**: Subjects will be questioned regarding adverse events in the form of non-leading questions (e.g., "How are you feeling?"). All adverse events will be assessed and documented and will be managed as per standard of care.
- 3.1.2.9 Concomitant medication (See section 3.1.1.12)
- 3.1.2.10 **Bland emollient collection:** Subjects will return with the bland emollient used over the past 7 days. The site staff will collect such as the subject should not use it while being treated with the study treatment.
- 3.1.2.11 Inclusion / Exclusion Criteria Evaluation (See section 4.1.)
- 3.1.2.12 **Randomization:** Subjects fulfilling inclusion and exclusion criteria will receive study product from the next available sequential randomized kit which contains one of the following three treatment arms:
 - > Test drug: Pimecrolimus Cream. 1%
 - ➤ Reference listed drug: Elidel® (Pimecrolimus) Cream 1%
 - ➤ Placebo: Vehicle of the test drug cream without Pimecrolimus

Each study product kit will contain three 100 gram tubes of study cream from the same randomized treatment arm. The kits will be packaged in a block size of 6. Each block will contain 2 kits of each treatment arm (2:2:2).

3.1.2.13 **Study Drug Dispensing:** Study drug tube(s) will be dispensed to each subject by a staff member delegated by the PI. The study drug dispenser will not participate in any clinical assessments. The delegated staff member will tear off the perforated label prior to dispensing to the subject. The perforated portion of the label contains the blinded treatment arm underneath an occlusive layer. The perforated label with blinded code will remain at the clinic site in case of emergency. (See section 6.5 regarding emergency unblinding.) The delegated staff member will dispense at least one tube of study cream.

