3.1.3 V3 - Follow up visit (Day 8 ± 3 days)

Subjects will return to the study site on day 8 with diary card. During this visit, the following procedures and evaluations will occur.

- 3.1.3.1 Signs and symptoms evaluation (See section 3.1.1.6)
- 3.1.3.2 BSA assessment (See section 3.1.1.7)
- 3.1.3.3 Investigator's global assessment (IGA) (See section 3.1.1.8)
- 3.1.3.4 Pruritus Assessment (See section 3.1.1.9.)
- 3.1.3.5 Local application site reactions (See section 3.1.1.10)
- 3.1.3.6 Adverse event assessment (See section 3.1.2.8)
- 3.1.3.7 Concomitant medication (See section 3.1.1.9)
- 3.1.3.8 **Assessment of Compliance:** The treatment diary card will be used to verify compliance. Compliance is defined in the term of study drug dose applied i.e. subject should apply the cream twice daily. The subjects should be using at least 75% and no more than 125% of expected study drug doses. If this is not the case, please decide if further study participation is recommended or if the subject should be re-instructed on proper study cream use and continued in the study.
- 3.1.3.9 **Study Drug Collection and Dispensing:** The delegated staff member will collect the used tube(s) from the subject. The used tube may be re-dispensed to the subject until fully used. A new tube from the subject kit may be provided if necessary. The subject should be reminded to return to the study clinic with all tubes at the next visit. Accountability of the dispensing of tubes will be recorded.
- 3.1.3.10 Diary Card Instructions / Schedule Next Visit (See section 3.1.2.13.)

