 care practices. If you use moisturizers, apply them after ELIDEL Cream, 1%.
- Call your doctor if your symptoms get worse with ELIDEL Cream, 1% or your symptoms do not improve after 6 weeks of treatment.

What should I avoid while using ELIDEL Cream, 1%?

- You should not use sun lamps, tanning beds, or get treatment with ultraviolet light therapy during treatment with ELIDEL Cream, 1%.
- Limit your time in the sun during treatment with ELIDEL Cream, 1% even when the medicine is not
 on your skin. If you need to be outdoors after applying ELIDEL Cream, 1%, wear loose fitting
 clothing that protects the treated area from the sun. Ask your doctor what other types of protection
 from the sun you should use. It is not known how ELIDEL Cream, 1% may affect your skin with
 exposure to ultraviolet light.
- Do not cover the skin being treated with bandages, dressings or wraps. You can wear normal clothing.
- ELIDEL Cream, 1% is for use on the skin only. Do not get ELIDEL Cream, 1% in your eyes, nose, mouth, vagina, or rectum (mucous membranes). If you get ELIDEL Cream, 1% in any of these areas, burning or irritation can happen. Wipe off any ELIDEL Cream, 1% from the affected area and then rinse the area well with cold water.
- Do not swallow ELIDEL Cream, 1%. If you do, call your doctor.
- · Avoid using ELIDEL Cream, 1% on skin areas that have cancers or pre-cancers.

What are the possible side effects of ELIDEL Cream, 1%?

ELIDEL Cream, 1% may cause serious side effects.

- See "What is the most important information I should know about ELIDEL Cream, 1%?"
- The most common side effect at the skin application site is burning or a feeling of warmth. These
 side effects are usually mild or moderate, happen during the first few days of treatment, and usually
 clear up in a few days.

Other common side effects include:

- headache
- · common cold or stuffy nose, sore throat
- cough
- flu (influenza)
- fever
- viral infection. Some people may get viral skin infections (like cold sores, chicken pox, shingles, or warts) or swollen lymph nodes (glands).

Tell your doctor if you get a skin infection or if you have any side effect (for example, swollen glands) that bothers you or that does not go away.

These are not all the possible side effects with ELIDEL Cream, 1%. Ask your doctor or pharmacist for more information.

Call your doctor for medical advice about side effects. You may report side effects to FDA at [name].

How should I store ELIDEL Cream, 1%?

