10.9.2 Application Site Reactions

Application site reactions including dryness, burning/stinging, erosion, edema, and pain, will be assessed based on Local Irritation Scale (LIS).

Application site reactions	0	1	2	3
	None	Mild	Moderate	Severe

Application site reaction scores will be summarized using frequency counts and percentages by visit for each treatment.

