Data Listing 16.2.5.2: Subject Treatment Diary Card All Randomized Subjects Randomized Treatment: [Pimecrolimus Cream, 1%][Elidel® (Pimecrolimus) Cream 1%][Placebo]

Medication Application	Medicatio	n Applied		Comments or Feeling of Discomfort Due to		
Date (Day)[1]	AM PM		Reason if Medication not Applied	Medication		
YYYY-MM-DD(1)	Y	Ν	XXXXXXX	XXXXX		
YYYY-MM-DD (XX)	Y	Y	NA	NA		
	Date (Day)[1] YYYY-MM-DD (1)	Date (Day)[1] AM YYYY-MM-DD (1) Y	Date (Day)[1] AM PM YYYY-MM-DD (1) Y N	Date (Day)[1] AM PM Reason if Medication not Applied YYYY-MM-DD (1) Y N XXXXXXX		

[1] Day is date minus Baseline date plus 1.

Generated on XX/XX/XX:XXXX by XXXXX / Uses: XX

	All Randomized Subjects Randomized Treatment: [Pimecrolimus Cream, 1%][Elidel® (Pimecrolimus) Cream 1%][Placebo]												
			Used Dru	ug Tubes	Unused/Pa	rtially Used I	Orug Tubes						
Subject Number	Visit	Date (Day)[1]	Collected?	Number Used	Collected?	Number Partially Used	Number unused	All Tubes Returned?/ Reason if Not	Study Drug Re- dispensed?/ Reason if Not	Dispensing Date			
XX-XXXX	Day 8	YYYY-MM-DD (XX)	Y	Х	Ν	0	0	No/ XXXXXXX	Yes/ NA	YYYY-MM-DD			
	Day 15	YYYY-MM-DD (XX)	Ν	0	Y	Х	Х	Yes/ NA	No/ XXXXX	NA			

Data Listing 16.2.5.3: Study Drug Accountability

Protocol No. CD-14-875

[1] Day is date minus Baseline date plus 1.

Generated on XX/XX/XX:XXXX by XXXXX / Uses: XX

Data Listing 16.2.6.1: Investigator's Global Assessment (IGA) All Randomized Subjects Randomized Treatment: [Pimecrolimus Cream, 1%][Elidel® (Pimecrolimus) Cream 1%][Placebo]

					Obse	rved	LOC	_	
Subject Number	Visit	Date (Day) [1]	Was IGA Performed?	Reason if not Performed	Overall IGA[2]	Change from Baseline[3]	Overall IGA	Change from Baseline	IGA Success on Day 15
XX-XXXX	Screening	YYYY-MM-DD (XX)	Yes	NA	2 – Mild	-	-	-	-
	U	YYYY-MM-DD (XX)	Yes	NA	2 - Mild	-	-	-	-
	Day 8	YYYY-MM-DD (XX)	Yes	NA	1 – Almost Clear	-1	-	-	-
	Day 15	YYYY-MM-DD (XX)	Yes	NA	XXXXXX	Х	XXXXXX	Х	Y

Note: Baseline is the last available measurement prior to first application of study medication. LOCF=Last Observation Carried Forward

[1] Day is date of visit minus Baseline date plus 1.

[2] Based on a 5-point scale of 0 (Clear) to 4 (Severe Disease).

[3] Indication: 2 = Worsen by 2 Points; 1 = Worsen by 1 Point; 0 = No Change; -1 = Improve by 1 Point; -2 = Improve by 2 Points; -3 = Improve by 3 Points

[4] LOCF results only present at Day 15

Data Listing 16.2.6.2: Individual Signs and Symptoms of AD
All Randomized Subjects

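### The scored comparison of application site reactions is likely to under-capture early burning/stinging, because the first post-dose score falls on Day 5 to 11 with no stated recall period

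*Protocol*

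**What the plan says.** **Role of the measure.** Protocol 2.2 includes comparing the safety and tolerability of test and reference. Protocol 3.3.2 lists the between-group comparison of application site reactions among the secondary endpoints. The synopsis describes that comparison as descriptive.

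**When it is scored.** The Local Irritation Scale (Appendix IV) grades five items from 0 to 3. Protocol 3.1.1.10 says: "At each study visit, the investigator will evaluate any application site reactions with separate severity scores for dryness, burning/stinging, erosion, edema, and pain". At Visit 2 the entry is "Local application site reactions (pre-treatment) (See section 3.1.1.10". At Visit 3, headed "V3 - Follow up visit (Day 8 ± 3 days", the entry is "3.1.3.5 Local application site reactions (See section 3.1.1.10", which adds no look-back. The last score is at Visit 4, Day 15 ± 3.

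**When reactions are expected.** The protocol introduction says: "Localized symptoms are most common during the first few days of Pimecrolimus Cream, 1% application and typically improve as the lesions of atopic dermatitis resolve". The Medication Guide in Appendix VII says of burning or warmth at the application site that such effects "happen during the first few days of treatment, and usually" are gone within a few days.

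**How it is analysed.** SAP 10.9.2: "Application site reaction scores will be summarized using frequency counts and percentages by visit for each treatment". Table 14.3.2 has columns for baseline, Day 8 and Day 15. It has no worst-post-baseline row and no within-subject change. Data Listing 16.2.5.2 shows a dated diary column headed "Comments or Feeling of Discomfort Due to" medication, but no summary table uses it.

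**The concern.** The dedicated tolerability instrument is first read after dosing at a point when, on the documents' own account, the typical reaction has passed its peak and may be over. A subject with moderate burning on Days 1 to 3 can score 0 at Visit 3. If that happens often, the by-visit table would show similar low burning rates in both active arms even if one cream stings more at first use, and this would read as comparable tolerability.

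The missing recall period also leaves sites to choose. Section 3.1.1.9 gives pruritus a 24-hour recall, while 3.1.1.10, directly after it, gives none. One site may ask about the whole interval and another may score only what is present that day, and the two kinds of score would then be pooled.

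A smaller issue concerns dryness, erosion and edema, which atopic dermatitis itself can produce. Each subject's baseline score is collected, but the planned table does not use it within subject. The SAP shells do show change from baseline for disease signs, body surface area and vital signs.

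**Working it through.** The documents give no sample size, power or expected rate for application site reactions, so there is no planned figure to reproduce. The check has three parts.

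**1. First post-dose score.** Visit 3 is Day 8 ± 3, so 8 − 3 = Day 5 to 8 + 3 = Day 11. Visit 2 is scored before treatment. No scheduled score falls on Days 1 to 4 after dosing.

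**2. Share of early reactions still present at a current-state score (illustration).** Assumptions: onset spread evenly over Days 1, 2 and 3, and duration D days. A reaction with onset day o is present on day d if o ≤ d ≤ o + D − 1.

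| Duration D (days) | Visit on Day 5 | Visit on Day 8 | Visit on Day 11 |
|---|---|---|---|
| 2 | 0% | 0% | 0% |
| 3 | 33% | 0% | 0% |
| 4 | 67% | 0% | 0% |
| 5 | 100% | 0% | 0% |
| 6 | 100% | 33% | 0% |
| 7 | 100% | 67% | 0% |
| 8 | 100% | 100% | 0% |

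For example, with D = 5 the latest onset (Day 3) ends on 3 + 5 − 1 = Day 7. Capture then depends on attending at the early edge of the window, or on reactions lasting longer than five days.

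**3. What partial capture does to the comparison.** Inputs: the label in Appendix VII gives application site burning on the reference product as 8% to 26% (10.4% in the 6-week pediatric trials, 25.9% in adults), and there are 216 subjects per arm. Expected cases scored per arm = 216 × rate × capture fraction. The yardstick is the exact power of a two-sided 5% Fisher test to detect a doubling of the reference rate. No such test is planned; it only shows how visible a difference would be.

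| Capture | Cases at 8% | Cases at 10.4% | Cases at 25.9% | Power, 10.4% doubled |
|---|---|---|---|---|
| 100% | 17.3 | 22.5 | 55.9 | 82% |
| 67% | 11.6 | 15.1 | 37.5 | 61% |
| 33% | 5.7 | 7.4 | 18.5 | 29% |
| 10% | 1.7 | 2.2 | 5.6 | 6% |

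At 33% capture, a true 10.4% versus 20.8% would be scored as about 0.33 × 10.4 = 3.4% versus 0.33 × 20.8 = 6.9%, so a gap of 10.4 points shrinks to about 3.4. At 8% doubled, the power falls from 69% at full capture to 21% at 33%. At 25.9% doubled, it falls from nearly 100% to 72%. The capture fractions and the doubling are assumptions.

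**The case against.** A reader might infer that the tolerability comparison misses its main event altogether. The documents do not support that.

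- **Adverse events carry a look-back.** Protocol 3.3.3 has subjects asked about health changes since the prior visit, which spans the first days of dosing. SAP 10.9.1 tabulates treatment-emergent events by arm and preferred term, with severity and causality, so burning reported as an event is shown by arm. The label's 8% to 26% are themselves adverse event rates, so adverse event reporting did find burning in those trials, although how it was elicited there is not stated. This stands. The route is weaker, however: Protocol 3.1.2.8 specifies non-leading questions, and the planned Fisher tests cover overall event categories, not burning.
- **The scale text does not exclude recall.** The global assessment is described as static and disease signs are scored as of the current visit, but no such limit is put on the irritation items. This stands: the text neither requires nor rules out asking about the interval. A score of 0 at Visit 3 after early burning is possible, not certain.
- **Duration is not given.** The protocol text says symptoms improve as lesions resolve; only the Medication Guide says they usually clear in a few days. Dosing also continues throughout. This stands, and it is why the loss cannot be sized.
- **Baseline is shown.** Table 14.3.2 prints baseline beside Day 8 and Day 15, and the arms are randomized. Pre-existing signs are therefore visible by group, and only the within-subject view is missing.
- **Other routes exist.** Unscheduled visits are allowed, though they would tend to catch the more troubled subjects, and Table 14.3.2 has no column for them. The diary field is dated, but Protocol 3.1.2.14 asks only for applied and missed doses. Appendix V was not available to check whether discomfort is prompted there.

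**Conclusion.** The point holds for the scored comparison: with the first post-dose score on Day 5 to 11, no stated recall and by-visit tables only, early burning/stinging is likely to be under-captured. This rests on the documents' own statements about timing. Early events still have a path through adverse event reports and the diary, but the first is unprompted and the second is not summarized.

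The size of the loss is unknown. Under the illustration above it runs from none (reactions lasting eight days or more with an on-schedule visit, or five days or more with a Day 5 visit) to complete (five days or less with an on-schedule visit). Those durations, the onset spread, the capture fractions and the doubling are all assumptions.

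The comparison is descriptive, and neither the equivalence decision nor the superiority tests use it. This is a cheap improvement to a stated secondary comparison, not a threat to the primary conclusion.

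**What to change.** **Protocol 3.1.1.10 and 3.1.3.5.** At Visit 3, record burning/stinging and pain twice: the current score, and the worst since first application. Compare the worst score between arms, not against each subject's own baseline. The baseline score has no such recall period, so subtracting it would inflate apparent worsening in every arm.

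**SAP 10.9.2.** Add by arm, each with the test-reference difference:

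- (a) the proportion of subjects with any diary-recorded discomfort due to medication on Days 1 to 7;
- (b) the proportion whose current-state score exceeds their own baseline, at each visit and at any post-baseline visit.

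**Cost.** One added question for two items at an existing visit, and a few table rows from data the plan already lists. The downsides are recall of up to about 10 days (Day 1 to Day 11) and the coding of free-text diary comments, whose rules should be fixed before unblinding.

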3.1.2 V2 - Baseline and Randomization Visit (Day 1)

The study specific procedures to be evaluated at baseline visit are:

- 3.1.2.1 Vital signs (See section 3.1.1.4)
- 3.1.2.2 Signs and symptoms evaluation (See section 3.1.1.6)
- 3.1.2.3 Body surface area assessment (See section 3.1.1.7)
- 3.1.2.4 Investigator's Global Assessment (IGA) (See section 3.1.1.8)
- 3.1.2.5 Pruritus Assessment (See section 3.1.1.9.)
- 3.1.2.6 Local application site reactions (pre-treatment) (See section 3.1.1.10)
- 3.1.2.7 **Urine pregnancy test** will be conducted for female subjects of child bearing age prior to dosing.
- 3.1.2.8 **Adverse Event Assessment**: Subjects will be questioned regarding adverse events in the form of non-leading questions (e.g., "How are you feeling?"). All adverse events will be assessed and documented and will be managed as per standard of care.
- 3.1.2.9 Concomitant medication (See section 3.1.1.12)
- 3.1.2.10 **Bland emollient collection:** Subjects will return with the bland emollient used over the past 7 days. The site staff will collect such as the subject should not use it while being treated with the study treatment.
- 3.1.2.11 Inclusion / Exclusion Criteria Evaluation (See section 4.1.)
- 3.1.2.12 **Randomization:** Subjects fulfilling inclusion and exclusion criteria will receive study product from the next available sequential randomized kit which contains one of the following three treatment arms:
 - > Test drug: Pimecrolimus Cream. 1%
 - ➤ Reference listed drug: Elidel® (Pimecrolimus) Cream 1%
 - ➤ Placebo: Vehicle of the test drug cream without Pimecrolimus

Each study product kit will contain three 100 gram tubes of study cream from the same randomized treatment arm. The kits will be packaged in a block size of 6. Each block will contain 2 kits of each treatment arm (2:2:2).

3.1.2.13 **Study Drug Dispensing:** Study drug tube(s) will be dispensed to each subject by a staff member delegated by the PI. The study drug dispenser will not participate in any clinical assessments. The delegated staff member will tear off the perforated label prior to dispensing to the subject. The perforated portion of the label contains the blinded treatment arm underneath an occlusive layer. The perforated label with blinded code will remain at the clinic site in case of emergency. (See section 6.5 regarding emergency unblinding.) The delegated staff member will dispense at least one tube of study cream.

Subjects (or guardians) will be instructed to apply a thin layer to the affected areas twice daily for 2 weeks (14 days). Subjects/guardians will be instructed about the following: When applying assigned study treatment after a bath or shower, the skin should be dry. Caregivers applying study treatment to a subject, or subject who is not

CONFIDENTIAL

Protocol Number: CD-14-875 Version 2.0

Dated 14 Oct 2016

treating their hands should wash their hands with soap and water after applying study treatment. Caregivers who are pregnant, breastfeeding or may become pregnant should consult their physicians and follow their recommendations relating to the potential exposure to Pimecrolimus 1% Cream. Appendix V Instructions for the Patients will be reviewed with the subject or guardian.

The subject will be instructed to return all tubes to the study clinic.

3.1.2.14 **Diary Card Instructions / Schedule Next Visit**: Subjects or their guardians will be issued a diary card with instructions to record all applied and missed doses.

